4.4.3 Data collection

We will collect patient sex, age, disease severity, comorbidities (smoking, diabetes, heart disease, lung disease, immunosuppression, etc.), other medications, and trial outcomes. A minimum of 50 patients in this trial will be swabbed on days 0, 1, 3, 5, 7, 10, 14 for quantitative polymerase chain reaction (PCR) assessment of viral titre. A minimum of 50 patients will have a blood sample collected on the day of randomization and on day 3. These samples will be used to measure inflammatory markers and ACE-2 levels and will be stored for future analyses.

4.5 Study Outcomes

4.5.1 Composite primary outcome

The primary outcome is mortality or need for invasive mechanical ventilation*.

*Patients intubated or requiring imminent intubation at the time of randomization will only be followed for the primary outcome of death.

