4.5.2 Secondary efficacy outcomes

The secondary outcomes are mortality, invasive mechanical ventilation, admission to ICU, renal replacement therapy, and extracorporeal support.

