4.6 Statistical Considerations

4.6.1 Sample size calculation

The minimum sample size required is **N=530** (265 in each intervention arm) in order to have 90% statistical power to detect a 40% relative risk reduction (RRR) in the proportion progressing to mechanical ventilation or death, assuming a standard-of-care risk of progression of 30%. Since patients will be hospitalized, we assumed minimal (<1%) loss to follow-up.

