4.6.2 Statistical analysis methods

The primary analysis of efficacy will be conducted under the intention-to-treat principle; all randomized participants will be included in the analyses. All results will be analyzed with 2-sided level of significance of 0.05. Given the rapid assessment of the primary outcomes of progression, and the expected absence of loss to follow-up, we will compare the proportions of progression events between the two study arms rather than the times to progressions. The primary analysis will use the Z-test for comparison of proportions. Secondary analyses will include adjusting the intervention effect for demographics, exposure characteristics, and severity of disease upon admission, using logistic regression models.

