4.6.3 Planned subgroup analyses

We will explore whether the following variables modify treatment effect: age, sex, disease severity (admission to ICU at randomization versus not) and presence or absence of comorbidities.

5. Program Management and Sub-studies

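### The inpatient primary endpoint turns on an undefined status, imminent intubation, that need not be recorded before allocation is known; the 90% power is not stated for the mixed endpoint that results

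*Protocol*

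**What the plan says.** Protocol 4.3 admits any adult who is in hospital, or waiting for a bed, with confirmed COVID-19. The exclusions in 4.3.2 concern G6PD deficiency and the study drugs; none concerns ventilation.

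Section 4.5.1 makes death or need for invasive ventilation the primary outcome, with this footnote: "Patients intubated or requiring imminent intubation at the time of randomization will only be followed for the primary outcome of death".

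Section 4.6.2 compares proportions with a single Z-test under intention to treat, so that "all randomized participants will be included in the analyses", and sets the test level: "All results will be analyzed with 2-sided level of significance of 0.05".

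Section 4.6.1 sizes the trial at 530 ("265 in each intervention arm") for 90% power to detect a 40% relative reduction "in the proportion progressing to mechanical ventilation or death, assuming a standard-of-care risk of progression of 30" percent. It makes no separate allowance for patients who are followed for death only.

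Randomization is stratified by site alone (4.2.3). The severity subgroup is ICU versus not (4.6.3). Neither separates patients by intubation status. Treatment is open-label, and sections 4.2.3 and 4.4.2 defend this by relying on objective outcome definitions and on ascertainment that does not depend on knowing the arm.

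**The concern.** For a patient who is intubated soon after entry, one classification decides whether that intubation is a primary event. If the patient was near intubation at randomization, it is not counted and only a later death is. If not, it counts.

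The protocol gives no criteria for being near intubation, names no assessor, and does not say when the status is entered. The words about the time of randomization fix the moment to which the status refers, not the moment at which it is written down. Section 4.4.3 collects disease severity, also without a time. A site may therefore complete the field after it has learned the arm, and perhaps after the intubation itself. That does not sit with the protocol's argument that objective definitions make up for the lack of blinding. If the arms are classified differently, the primary comparison is biased. No later analysis plan can repair this if the status was not captured beforehand.

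A second matter follows from the same footnote. The power statement is worded for patients who can progress to ventilation or death, whereas the analysed endpoint mixes them with patients who can contribute only death.

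**Working it through.** **Inputs from the protocol.** Two-sided 0.05 and Z-test (4.6.2); 265 per arm, control risk 30%, relative reduction 40%, so 18% on AZCT (4.6.1).

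**Assumptions, not in the protocol.** The number of patients relabelled; their mortality (30-50%); the share of death-only patients (20% in the table below); their control mortality (30-50%); the effect on death in them.

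**1. The protocol's own figure.** Pooled-variance formula, mean risk 0.24:

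n = [1.960·√(2·0.24·0.76) + 1.2816·√(0.30·0.70 + 0.18·0.82)]² / 0.12²
= (1.960·0.6040 + 1.2816·0.5980)² / 0.0144 = 264.1, so 265 per arm.

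Power at 265 per arm is 90.1%. The stated 530 reproduces exactly.

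**2. Relabelling with no true effect.** Expected events per arm are 265 × 0.30 = 79.5. Suppose k intubated AZCT patients are called near-intubation after the fact and a proportion d of them die. Deaths still count, so the events lost are k(1 − d). The false-positive rate is the chance that the Z-test rejects in favour of AZCT:

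Φ{[(0.30 − p) − 1.960·√(2p̄(1 − p̄)/265)] / √([0.30·0.70 + p(1 − p)]/265)}

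Here p is the observed AZCT risk and p̄ the mean of 0.30 and p.

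| k | d | AZCT events | p | Risk ratio | False positive for AZCT |
|---|---|---|---|---|---|
| 0 | – | 79.5 | 0.300 | 1.00 | 2.5% |
| 8 | 0.5 | 79.5 − 4.0 = 75.5 | 0.285 | 0.95 | 5.7% |
| 8 | 0.3 | 79.5 − 5.6 = 73.9 | 0.279 | 0.93 | 7.7% |
| 13 | 0.5 | 79.5 − 6.5 = 73.0 | 0.275 | 0.92 | 9.1% |
| 13 | 0.3 | 79.5 − 9.1 = 70.4 | 0.266 | 0.89 | 13.9% |

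Thirteen patients are 4.9% of an arm (13/265). Relabelling in the usual-care arm would push the result the other way.

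**3. Power for the mixed endpoint.** With a death-only share of 20%, control mortality m and relative reduction in death r in that group:

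control risk = 0.8·0.30 + 0.2·m; AZCT risk = 0.8·0.18 + 0.2·m·(1 − r)

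| m | r = 0 | r = 20% | r = 40% |
|---|---|---|---|
| 30% | 0.300 vs 0.204: 72.2% | 0.300 vs 0.192: 82.5% | 0.300 vs 0.180: 90.1% |
| 40% | 0.320 vs 0.224: 70.1% | 0.320 vs 0.208: 83.5% | 0.320 vs 0.192: 92.4% |
| 50% | 0.340 vs 0.244: 68.2% | 0.340 vs 0.224: 84.5% | 0.340 vs 0.204: 94.3% |

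Across shares of 10-30% and control mortality of 20-50%, power runs from about 55% (30% share, 50% mortality, no effect on death) to about 96% (30% share, 50% mortality, 40% reduction). The footnote can therefore move power in either direction.

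**The case against.** The best defence is that the footnote ties the status to randomization, and that a central system with undisclosed block sizes conceals the arm until assignment. To call an intubation hours later imminent would misapply the rule. This stands as far as it goes: a reader might infer that an unblinded judgement does decide which intubations count, but the protocol does not say so. It leaves the possibility open because it requires neither a definition nor recording before allocation.

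A reader might also infer that the trial is underpowered. The documents do not support that. The 530 reproduces; progression includes death, which ventilated patients can show; and with a 40% reduction in death and control mortality of at least 30%, power is 90-96%. The figures near 70% need no effect on death at all. Section 4.3.3 also admits that progression rates are poorly known and lets the sample size grow. That covers an uncertain event rate but does not describe the mixed endpoint.

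A third tempting inference is that baseline ventilation or ICU stay will dilute the secondary outcomes. Section 4.5.2 only lists them: "The secondary outcomes are mortality, invasive mechanical ventilation, admission to ICU, renal replacement therapy, and extracorporeal support". Nothing says that a state present at entry is counted as an event, and the sentence on all randomized participants concerns the primary analysis. Who is at risk for these outcomes can be left to the analysis plan.

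The protocol does plan a secondary adjustment for severity on admission, an ICU subgroup, and mortality as an outcome in its own right. These help a reader examine the mixture, but they do not protect the classification on which the primary endpoint depends.

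**Conclusion.** The point holds as an unprotected classification in the primary endpoint of an open-label trial. The size of any bias is illustrative, since it depends on assumed counts, on all relabelling falling in one arm and on 30-50% mortality. Within those assumptions, 8 patients are enough to raise the false-positive rate favouring AZCT from 2.5% to about 6-8%, and 13 to about 9-14%. There is no evidence that such relabelling would occur.

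The power statement is correct arithmetic for a 30% risk and a 40% reduction overall. It is incomplete because it does not say that these figures must hold for the mixed endpoint as a whole. The protocol gives neither the share nor the mortality of the death-only group, so no single corrected power can be given.

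**What to change.** 1. Define imminent intubation by stated, objective criteria.
2. Record the status (intubated, imminent by that definition, or neither) in the randomization system before the allocation is released. Use only that recorded value to decide which primary endpoint applies.
3. Stratify the primary comparison by the recorded status, and report the death-only stratum separately.
4. State in 4.6.1 that 90% power at 530 assumes a 30% control risk and a 40% relative reduction for the mixed endpoint as a whole, and add the sensitivity shown above. It would be wrong to say instead that the 90% applies to patients not intubated at entry: with 20% intubated, 0.8 × 265 = 212 per arm remain and power is 82.7%.

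Dropping the imminent category altogether would also remove the judgement. It would, however, count intubations that treatment may have had no time to prevent, so it is a trade-off and not a necessary correction.

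The cost is one field in the randomization system, some amendment wording, slightly more analysis work, and a power statement that may look less favourable. The recording and stratification need no extra patients.

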4.5.2 Secondary efficacy outcomes

The secondary outcomes are mortality, invasive mechanical ventilation, admission to ICU, renal replacement therapy, and extracorporeal support.

4.5.3 Tertiary efficacy outcomes

Tertiary outcomes are length of ICU stay, length of hospital stay, noninvasive mechanical ventilation, and duration of mechanical ventilation.

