3.5 Study Outcomes

3.5.1 Primary efficacy outcome

The primary outcome is admission to hospital or mortality.

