3.5.3 Tertiary efficacy outcomes

Tertiary outcomes are length of ICU stay, length of hospital stay, noninvasive mechanical ventilation, and duration of mechanical ventilation.

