3.7 Statistical Considerations

3.7.1 Sample size calculation

The total minimum sample size required is **N=1000** (500 in each intervention arm) in order to have 90% statistical power to detect a rate ratio (RR) of 0.50 in the time to progression to requiring hospitalization or death, assuming a standard-of-care rate of progression of 12%. We also assumed an accrual time of 3-6 months and make allowance for cumulative loss to follow-up of 3% per arm although we expect this will be lower (i.e., <1%).

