3.7.2 Statistical analysis methods

The primary hypothesis of efficacy will be conducted under the intention-to-treat principle; all randomized participants will be included in the analyses. All results will be analyzed with 2-sided level of significance of 0.05.

Given the fixed 45 day time period of assessment of the primary outcomes of progression, we will compare the proportions of progression events between the two study arms rather than the times to progression. The primary analysis will use the Z-test for comparison of proportions. We will also secondarily adjust the intervention effect for demographics, and exposure characteristics of participants, using logistic regression models.

Descriptively, Kaplan-Meier curves of the estimated time to hospitalization will be constructed. This secondary analysis will use the Log-rank statistic, stratified by center. Secondary analyses will include adjusting the intervention effect for demographic and exposure characteristics of the participants using Cox proportional hazards regression models.

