4.1.3 Tertiary efficacy objectives

To evaluate if AZCT compared to usual care results in reductions in length of ICU stay, length of hospital stay, non-invasive ventilation, and duration of ventilation.

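### The outpatient time-to-event analysis drops death from the primary endpoint, and the tertiary durations in both trials count a shorter stay as benefit without regard to death

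*Protocol*

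**What the plan says.** **Outpatient time-to-event analysis.** Protocol 3.5.1 defines the endpoint: "The primary outcome is admission to hospital or mortality". Section 3.7.1 gives the sample size as that needed "to detect a rate ratio (RR) of 0.50 in the time to progression to requiring hospitalization or death". Section 3.7.2 makes a Z-test of proportions the primary analysis and then adds: "Descriptively, Kaplan-Meier curves of the estimated time to hospitalization will be constructed". It continues: "This secondary analysis will use the Log-rank statistic, stratified by center". A covariate-adjusted Cox model follows in the same paragraph. That paragraph does not mention death as an event, a competing event or a reason for censoring.

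**Durations.** In the inpatient trial, section 4.1.3 asks whether treatment "results in reductions in length of ICU stay, length of hospital stay, non-invasive ventilation, and duration of ventilation", and section 4.5.3 lists the matching outcomes: "Tertiary outcomes are length of ICU stay, length of hospital stay, noninvasive mechanical ventilation, and duration of mechanical ventilation". The outpatient trial has the same objective in 3.1.3 and the same outcomes in 3.5.3 ("Tertiary outcomes are length of ICU stay, length of hospital stay" and so on). None of these sections says how a patient who dies is counted. Sections 3.7.2 and 4.6.2 apply a two-sided 0.05 level to all results.

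**The concern.** A time-to-event analysis placed beside the primary comparison is normally read as support for it. Here it addresses a different endpoint. Under an ordinary Kaplan-Meier and log-rank analysis in which only hospitalization is an event, an outpatient who dies at home leaves the risk set without contributing one. If treatment moved some patients from admission to death before admission, the curve would improve.

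The durations raise a related problem. The objectives fix the direction of benefit (shorter is better), but a patient who dies early also has a short stay and a short time on the ventilator. In the outpatient trial most participants are expected to have no stay. A comparison restricted to those admitted would compare groups selected by the very event that treatment is meant to prevent.

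**Working it through.** **1. The plan's own sample sizes.** Pooled Z-test, two-sided 0.05, 90% power:

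n per arm = [1.960·√(2p̄(1−p̄)) + 1.282·√(p₁(1−p₁)+p₂(1−p₂))]² / (p₁−p₂)²

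- Outpatient, 12% vs 6%: 477 per arm, 954 in total. With 3% loss, 954/0.97 ≈ 984, close to the stated 1000. Power at 500 per arm is 91.3%.
- Outpatient, log-rank (Schoenfeld), ratio 0.50: 4(1.960+1.282)²/(ln 0.5)² gives 88 events. 88/0.09 ≈ 978 patients, and 978/0.97 ≈ 1008, also close to 1000.
- Inpatient, 30% vs 18%: 265 per arm, an exact match to 530.

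These figures concern the composite endpoints, so nothing below changes them.

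**2. Power of the log-rank on hospitalization alone.** Expected composite events are 0.12×500 + 0.06×500 = 60 + 30 = 90. Power = Φ(|ln 0.5|·√D/2 − 1.960).

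- D = 90: Φ(3.288 − 1.960) = 0.908.
- Assume 10% of composite events are deaths without admission, so D = 81: Φ(3.119 − 1.960) = 0.877.

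**3. Direction of the log-rank.** The documents give no rate of death before admission, so a range is assumed. Take 12% admissions under usual care, and let each extra death on active treatment replace an admission. Then HR ≈ ln(1−p_T)/ln(1−p_C), where p is the admission risk, and Z = −ln(HR)·√(D/4) with D = 500(p_C+p_T).

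| Deaths before admission (usual care vs active) | Admissions | Composite, each arm | Apparent HR | Z |
|---|---|---|---|---|
| 0.1% vs 0.2% | 12.0% vs 11.9% | 12.1% | 0.99 | 0.05 |
| 0.5% vs 1% | 12.0% vs 11.5% | 12.5% | 0.96 | 0.25 |
| 1% vs 2% | 12.0% vs 11.0% | 13.0% | 0.91 | 0.50 |
| 1% vs 4% | 12.0% vs 9.0% | 13.0% | 0.74 | 1.56 |

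If death is instead independent of the risk of admission, the hospitalization hazard ratio stays at 1.00.

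**4. Direction of length of stay.** With equal discharge times for survivors in both arms, the difference in mean stay ≈ (difference in mortality) × (mean day of death − mean day of discharge). All rates and days are assumed.

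- Death day 8, discharge day 12, mortality 20% vs 12%: mean stay is 0.20×8 + 0.80×12 = 11.2 days with usual care and 0.12×8 + 0.88×12 = 11.5 with the better treatment, the wrong direction. Days alive and out of hospital to day 45, death scored 0, are 0.80×33 = 26.4 vs 0.88×33 = 29.0, the right direction.
- Simulations with control mortality of 10–20% and 1.25 to 1.5 times that on active treatment: with death day 8 and discharge day 14, stay is 0.16 to 0.60 days shorter in the arm with more deaths. With both at day 10, the difference is about 0. With death day 14 and discharge day 10, stay is 0.11 to 0.38 days longer. Days alive and out of hospital are worse in the arm with more deaths in every scenario, by 0.8 to 3.5 days.

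**5. Outpatients with no stay.** At most 60 + 30 = 90 of 1000 are expected to reach the composite, so at least 910 (91%) are expected to have no admission. The 60 and 30 include deaths without admission and are therefore upper limits for admissions.

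**The case against.** The strongest reply is that a rule for deaths in duration summaries commonly belongs in the statistical analysis plan, which may exist but is not available here. Sections 3.5.3 and 4.5.3 only list outcomes, so their silence does not show that deaths will be mishandled. That stands, and it is why the durations are the lesser point. What the protocol does fix is the direction of benefit.

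Hospital admission is also a secondary outcome in its own right (3.5.2), so an analysis of time to hospitalization has a legitimate target, and the curves are introduced as descriptive. That stands too. But the log-rank test is labelled secondary, and 3.7.2 contains no time-to-event analysis of the endpoint that 3.7.1 describes.

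The sizes are modest. A 0.3-day difference in stay with a standard deviation of about 7 and 265 per arm has a standard error of 7×√(2/265) ≈ 0.6 day, so Z is about 0.5. The fall in power from 91% to 88% is small.

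Several stronger readings are tempting, and the documents do not support them:

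- That the protocol censors deaths. It does not say so; this follows only from applying the method as written.
- That a harmful arm will look better. This needs deaths to replace admissions, or deaths to come earlier than discharge would have.
- That excess deaths would be hidden. Death is part of both primary composites, and mortality is a separate secondary outcome in both trials. Where deaths replace admissions one for one, the outpatient composite is level and the mortality outcome shows the excess.

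**Conclusion.** The mismatch within the outpatient trial is real: sections 3.5.1 and 3.7.1 include death, and the time-to-event analysis in 3.7.2 does not. As written, that analysis does not support the primary endpoint. Any distortion is slight (apparent hazard ratio 0.91 to 0.99) while deaths before admission are at most 1% vs 2%, and becomes material (0.74) only at about 1% vs 4%. These rates are assumptions, and the result also requires deaths to replace admissions.

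The tertiary durations are open to misreading because shorter is defined as better while an early death also shortens them. The sign of the bias depends on the timing of deaths, which the documents do not give. This is worth amending, but it is confined to supportive and tertiary results. The primary Z-tests, the separate mortality outcomes and both sample sizes stand.

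**What to change.** In section 3.7.2, make the Kaplan-Meier, log-rank and Cox analyses use time to first hospitalization or death. If hospitalization alone is also wanted, show it as cumulative incidence with death as a competing event. This is a one-line change that needs no further data.

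In both trials, analyse the tertiary durations as days alive and out of hospital, out of ICU and free of ventilation to day 45, in all randomised patients. Rank death worst; patients never admitted or never ventilated take the maximum on the relevant measure. A rank test stratified by site, matching the randomization, would suit. Keep raw durations as description.

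The second change redefines outcomes as well as wording. It relies on the dates that a length of stay or duration of ventilation already requires, within the existing 45-day follow-up. Its small drawback is that a composite of survival and stay measures resource use less directly, which is why the raw durations should still be reported. No change in sample size is needed.

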4.5.4 Translational outcome

The translational outcomes are viral titre, inflammatory markers, and ACE-2 receptor levels.

4.5.5 Safety outcomes

The safety outcomes are malignant arrhythmia requiring intervention, agranulocytosis, and Stevens-Johnson syndrome/toxic epidermal necrolysis, and retinal toxicity.

4.5.6 Safety outcome definitions

Malignant arrhythmia requiring intervention: Life-threatening ventricular arrhythmias: Regular, wide complex tachycardia lasting at least 30 seconds or associated with hemodynamic instability, polymorphic ventricular tachycardia (including torsades de pointes) of any duration, ventricular fibrillation of any duration requiring intervention.

Agranulocytosis: severe neutropenia, neutrophils below 500 cells/mm³ of blood.

Stevens-Johnson syndrome/Toxic epidermal necrolysis: fever, mucositis, skin tenderness, and blistering.

Retinal toxicity: New onset loss of vision with associated bilateral change of retinal pigmentation (Bull's-eye maculopathy).

4.6 Statistical Considerations

4.6.1 Sample size calculation

The minimum sample size required is **N=530** (265 in each intervention arm) in order to have 90% statistical power to detect a 40% relative risk reduction (RRR) in the proportion progressing to mechanical ventilation or death, assuming a standard-of-care risk of progression of 30%. Since patients will be hospitalized, we assumed minimal (<1%) loss to follow-up.

